47 48 Standard treatment for Sever's disease is placement of heel cups in shoes and stretching or 49 physical therapy. These interventions are effective in reducing Sever's patients' heel pain.¹²⁻¹⁶ A 50 retrospective study showed that with treatment with a heel cup or other foot orthoses, symptoms improved within 2 months.⁸ However, there remains a distinct lack of randomized control trials 51 evaluating treatments for Sever's in the literature.¹⁷ For the many young athletes with Sever's who 52 53 participate in barefoot sports such as gymnastics, dance, or tae kwan do, the standard treatment is 54 inadequate. They cannot use the recommended heel cups, which are placed in an athletic shoe. 55 Currently, two braces are commonly used for barefoot athletes with Sever's: Cheetah Heel Cups 56 and The X Brace. Neither of these braces are currently FDA approved as they are not considered 57 medical devices and are marketed as an insert. Health care providers often recommend barefoot 58 athletes purchase these braces, but no published studies evaluating their effectiveness exist in the 59 established literature. This study will compare these two braces in an investigator-blinded, 60 randomized control trial in order to contribute to the understanding of standard treatment for 61 barefoot athletes with Sever's disease and improve patient outcomes by affecting clinical practice. 62 In light of the paucity of information on and the importance of optimizing patient outcomes to 63 improve quality of life and maintain an active lifestyle for young barefoot athletes, this prospective, 64 randomized treatment study will compare the effectiveness of two braces in decreasing pain 65 severity in barefoot athletes diagnosed with Sever's disease. 66 67 III. Preliminary Studies/Progress Report: 68 No preliminary studies have been conducted at this institution. 69 70 IV. Research Methods 71 A. Outcome Measures: 72 i. Primary Outcome: Oxford Ankle Foot Questionnaire for Children (OxAFQ-C) Scores 73 ii. Visual Analog Scale (VAS) Pain Score 74 iii. Subject-Reported Compliance with Brace Use 75 1. Hours per week the brace was worn with barefoot sport activity 76 iv. **Rest from Sport** 77 1. Amount of time per week taken off from barefoot sport due to pain (if 78 applicable) 79 Acceptability of Brace ν. 80 1. Comfort (Comfortable: Y/N) 81 2. Appearance (Acceptability: Y/N) 82 3. Perceived Effect on Athletic Performance (Improvement: Y/N) 83 Pain Medicine Usage vi. 84 1. Weekly dosage of pain medicine (if applicable) 85 B. Explanatory Variables: 86 i. Demographic 87 1. Name and Medical Record Number 88 2. Date of Birth 89 3. Age at time of visit

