152	b. Assent will be sought from athletes younger than 13 years of age.
153	c. Consent will be sought from parents of subjects ages 7-14.
154	4. [name] or designated staff will answer any questions after the patient and
155	his or her parents have read and reviewed the informed consent and assent
156	forms. It will be emphasized to the patients that their decision to participate in
157	the study will in no way impact their treatment. Comprehension will be
158	assessed by reviewing the consent forms with the patient and his or her parents
159	thoroughly and asking the subjects questions requiring more than a simple
160	yes/no answer.
161	a. Patients and parents will sign the appropriate line on the informed
162	consent/assent form.
163	b. Consent procedures will take place in a private room or over a private
164	call.
165	5. Subject will complete initial demographics survey, OxAFQ-C, and VAS.
166	6. Subject will be randomized into either the Cheetah Heel Cup or The X Brace
167	treatment group. The randomization scheme will be independently created by
168	the research assistant. The random assignment will be kept blind to the PI and
169	statistician.
170	7. Subject will receive their assigned brace in the mail following their consent visit.
171	Subjects will receive an activity and rest log in the mail with their
172	brace. This is a weekly log and will help subjects track their weekly
173	activity in their barefoot sport (in hours), amount of time spent in
174	brace during barefoot sport (in hours), and any rest time taken from
175	their barefoot sport (in hours). This log is optional, but encouraged,
176	to fill out as it will not be submitted to the researchers. The
177	intended purpose of the log is to aid in answering the monthly
178	questionnaire on weekly activity, time in brace, and rest time.
179	8. At 1, 2, and 3 months, a study team member will email the subject's parent the
180	OxAFQ-C, VAS and questionnaire on activity/brace usage. During this time,
181	subjects will also answer questions pertaining to pain medicine use and any
182	adverse outcomes from brace use. A reminder phone call will be made if the

183 184 185 186 187		iv.	questionnaires have not been completed within 5 days. Subjects will not be seen after the visit where consent was obtained, unless an adverse outcome arises requiring an assessment by [name].Planned Duration of Study1. Two-years from COMIRB approval date to allow for adequate enrollment

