- 283 i. Sample Size: We will use a linear mixed model to test the null hypothesis that the 284 difference in OxAFQ-C physical domain scores between the The X Brace and 285 Cheetah Heel Cups does not depend on time (group*time interaction). Means for 286 treatment group at each time point were estimated based on a related RCT by James et al. ¹³. The common standard deviation for all OxAFQ-C physical domain 287 scores was assumed to be 6 and the correlation between time consecutive points 288 289 was conservatively assumed to be 0.6 based on this previous RCT. We intend to 290 use a one-to-one block randomization scheme to ensure equal allocation of 291 patients to each treatment group. Assuming a Type 1 error rate of 0.05, a sample 292 size of 44 participants total, 22 in each group, will provide 0.9 power to reject the 293 null hypothesis of no group*time interaction based on the Hotelling-Lawley test 294 statistic with an alpha level of 0.05. Assuming there is no missing data, no time 295 varying covariates, and the repeated measures are consistently collected (general 296 linear mixed model reversibility criteria is met), the Hotelling-Lawley trace statistic 297 is equivalent to the statistical test, the Wald statistic with Kenward-Roger degrees of freedom, described in the data analysis plan.²⁰. With an expected 30% loss to 298 299 follow up, we will inflate the sample size to account for attrition, for a total 300 enrollment goal of 58. The clinic treats 10 barefoot athletes with a clinical 301 diagnosis of Sever's Disease who meet the eligibility criteria for this study each 302 month. We expect a consent rate of approximately 50%. At an effective enrollment 303 rate of 5 patients per month, we will reach the enrollment goal of 58 participants 304 within 12 months. All samples size calculations were performed with GLIMMPSE, 305 an internet based open source software program capable of computing power and 306 sample size for multi-level and longitudinal research designs²¹
- 307 308
- 309

310 311 Table 1. Expected OxAFQ-C physical domain scores based on data from James et al^{13}

Treatment	1 month	2 months	3 months
Cheetah Heel Cups	67 (±6)	83 (±6)	85 (±6)
The X Brace	64 (±6)	82 (±6)	78 (±6)

312 313

314

315

316

317

318

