iii. Analysis Plan: Demographic and clinical characteristics will be summarized and compared between the two treatment groups using chi-squared and two-sample ttests for categorical and continuous data, respectively. Imbalance between groups will be adjusted for in subsequent statistical analyses. For hypothesis 1, Linear mixed model regression analyses will be used to compare group differences

ii.

319 (Cheetah Brace vs X brace) across the 1, 2 and 3 month visits. We will test the null 320 hypothesis that the difference between groups does not depend on time 321 (group*time interaction). The parameter estimate will be tested using the Wald 322 statistic with Kenward-Roger degrees of freedom and an alpha level of 0.05. 323 Intent-to-treat analyses will be performed for all the primary outcome variables. A 324 per-protocol analysis will also be performed. For the secondary analysis, the other 325 two domains of the OxAFQ-C questionnaire as well as VAS pain scores will be 326 analyzed using separate linear mixed models that iwill also test the group*time 327 interaction. Linear regression models will also be used to compare overall 328 compliance. Logistic regression models will be used to test the null hypothesis of 329 no difference between groups for each of the three brace acceptability metrics 330 (comfort, appearance, and perceived effect on athletic performance).

331

334

335

336

337

338

339

340

341 342

343

344

345

350

332 333

G. Summarize Knowledge to be Gained:

It is common practice to provide heel cups and stretching exercises for patients with Sever's. Because these heel cups cannot be used in barefoot athletes, alternative braces are used. Currently, there are two commonly used braces in barefoot athletes, Cheetah Heel Cups and the The X Brace. No previous study has looked at the effectiveness of these braces. This study would compare these braces in a blinded clinical trial to determine if these braces are effective and if one brace is more effective in decreasing severity of pain in barefoot athletes with Sever's. This study will contribute to the understanding of treatment for barefoot athletes with Sever's disease and will improve patient outcomes by affecting clinical practice. In order to improve quality of life and allow young athletes to remain active, this prospective, randomized treatment study will compare the effectiveness of two braces in decreasing pain severity in barefoot athletes diagnosed with Sever's disease.

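### Monthly brace hours are compared by ordinary linear regression of an undefined overall value; a mixed model using every returned month would be slightly more precise, and would avoid bias if loss differs by arm while hours change over time

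*Combined protocol and SAP*

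**What the plan says.** Outcome Measures (IV.A) defines compliance as "Hours per week the brace was worn with barefoot sport activity", reported by the subject. Methods step 8 (IV.D.iii) sets three reports per child: "At 1, 2, and 3 months, a study team member will email the subject's parent the" survey, whose content is "OxAFQ-C, VAS and questionnaire on activity/brace usage". Compliance is therefore collected on the same schedule and form as the OxAFQ-C and VAS.

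The Analysis Plan (IV.F.iii) treats these outcomes differently. For the secondary outcomes, the other "two domains of the OxAFQ-C questionnaire as well as VAS pain scores will be" "analyzed using separate linear mixed models". The next sentence gives compliance a different method: "Linear regression models will also be used to compare overall" compliance. It does not say how three monthly values become one overall value, or what happens when a month is missing. The intent-to-treat statement covers the primary outcome only: "Intent-to-treat analyses will be performed for all the primary outcome variables".

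Sample Size (IV.F.i) expects substantial attrition: "With an expected 30% loss to" follow-up. It gives no split by month or by arm.

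**The concern.** A linear regression with one value per child needs a summary of up to three reports. With 30% of children expected to be lost, two summaries fit the wording. One is the mean of whatever months came back. The other is the three-month mean in children who returned all three.

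The first sets one child's month-1 value beside another child's three-month average. This is harmless on average if the mix of months is the same in both arms. It is not harmless if one arm loses more children early and brace hours drift over time. The second discards the reports of children who left. A mixed model needs neither compromise and is already planned for the outcomes on the same form.

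At stake is the size and precision of one secondary comparison between the braces. The primary test is untouched.

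**Working it through.** The documents give no numerical target, SD or power for compliance, so there is no figure of the plan's own to reproduce.

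**Inputs from the documents:** three monthly reports (IV.D.iii step 8); 58 children allocated 1:1, so 29 per arm; 30% loss overall; correlation 0.6 (IV.F.i, where it is assumed for OxAFQ-C physical scores at consecutive times and is borrowed here).

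**Assumed:** SD 3 h/week; equal correlation between months; no true brace difference; hours falling by *d* = 1, 2 or 3 h per month (6-5-4, 6-4-2, 8-5-2); half of lost children leaving after month 1 and half after month 2; loss unrelated to the hours themselves; loss of 30% v 30%, 40% v 20% or 45% v 15%.

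**Step 1: bias of the mean of available months.** Relative to the three-month average, a child lost after month 1 is too high by *d*, and a child lost after month 2 by *d*/2. An arm losing a share *p* is therefore too high by (p/2)d + (p/2)(d/2) = 0.75·p·d. The false difference between arms is 0.75·d·(p₁ − p₂).

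- 30% v 30%: 0 for every *d*.
- 40% v 20%: 0.75 × 0.20 × d = 0.15, 0.30, 0.45 h/week.
- 45% v 15%: 0.75 × 0.30 × d = 0.225, 0.45, 0.675 h/week.

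If hours rise instead, *d* is negative and the false difference changes sign.

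**Step 2: standard errors with equal 30% loss.** The variance of a child's mean over *k* months is 9[1 + 0.6(k − 1)]/k, which is 9, 7.2 and 6.6 for k = 1, 2, 3. Weighted 0.15, 0.15 and 0.70, this averages 7.05. Mixing months adds the variance of the excesses in step 1: 0.15d² + 0.15(d/2)² − (0.225d)² = 0.137d².

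- Mean of available months: √[2(7.05 + 0.137d²)/29] = 0.704, 0.724, 0.756.
- Completers only, 29 × 0.7 = 20.3 per arm: √(2 × 6.6/20.3) = 0.806.
- Mixed model with month factor and group main effect: average information per child is 0.15/9 + 0.15/7.2 + 0.70/6.6 = 0.1436, so the standard error is √[2/(29 × 0.1436)] = 0.693.

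The mixed model's standard error is 1.6%, 4.3% and 8.3% smaller than that of the mean of available months (0.693/0.704, 0.693/0.724, 0.693/0.756). It is 14% smaller than for completers only (0.693/0.806). Simulation gives about 2–8% and 13–16%.

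**Step 3: false-positive rate with unequal loss.** The rate is Φ(−1.96 + b/SE) + Φ(−1.96 − b/SE), with *b* from step 1. The SE is recomputed with each arm's own loss: the within-child part totals 14.1 over the two arms in both settings, and the mixing part totals 0.2625d² (40% v 20%) or 0.2484d² (45% v 15%).

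| Loss | d | b | SE | False-positive rate |
|---|---|---|---|---|
| 40% v 20% | 1 | 0.15 | 0.704 | 5.5% |
| | 2 | 0.30 | 0.723 | 7% |
| | 3 | 0.45 | 0.753 | 9% |
| 45% v 15% | 1 | 0.225 | 0.703 | 6% |
| | 2 | 0.45 | 0.721 | 10% |
| | 3 | 0.675 | 0.751 | 15% |

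In simulation under the same assumptions the mixed model has bias of about 0 and a false-positive rate of about 4–5%.

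**The case against.** The strongest reply is that the plan has an undefined term, not a wrong analysis. Linear regression on one summary per child is a valid method. With equal loss unrelated to the outcome it is unbiased and keeps its nominal error rate. That stands. Three stronger readings are tempting, and the documents do not support them.

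- A reader might infer that 30% loss by itself biases the comparison. It does not: step 1 gives zero when loss is equal. Bias in this calculation needs unequal loss and a time trend together, and the documents state neither.
- A reader might infer that the three reports will be entered as independent rows, giving standard errors that are too small. The plan does not say so. An overall value most naturally means one per child, and the preceding sentence uses mixed models for repeated outcomes.
- A reader might infer that compliance will decide whether a brace failed or was simply not worn. The Analysis Plan gives it no such role and does not tie the per-protocol analysis to it.

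The size of the bias is also open to challenge. Loss of 45% v 15% is a threefold difference. A mean of 2 h with SD 3 would put about a quarter of a normal distribution below zero, so the steepest trend is stretched. Children who return no survey at all enter neither analysis, so placing all loss after month 1 or 2 enlarges the effect. Hours could also rise as children return to sport, which reverses the direction.

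What remains is that both conditions are plausible. Follow-up is meant to span symptom resolution (IV.D.v), time off sport because of pain is a separate outcome (IV.A), and an adverse reaction to a brace can end participation (IV.E.iii). A defined summary with a missing-month rule would close the gap in wording, but would still give up precision or leave the exposure to unequal loss.

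**Conclusion.** The point holds as a modest improvement to one secondary analysis. With equal loss the planned comparison is unbiased, and the gain from a mixed model is small: about 2–8% in standard error against a mean of available months, and about 13–16% against completers only.

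With unequal loss and changing hours, the mean of available months is biased by about 0.15–0.45 h/week (40% v 20%) or 0.2–0.7 h/week (45% v 15%), and the false-positive rate is about 5–15%. A completers-only summary stays unbiased under the same random loss, at its cost in precision.

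These sizes rest on the assumed SD, trend, timing of loss and arm-specific loss, and on a correlation borrowed from another outcome. In the settings examined the mixed model was never worse.

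**What to change.** In IV.F.iii, replace the linear regression for compliance by a linear mixed model of monthly brace hours, with month as a three-level factor, a group main effect and within-child covariance, using all returned months. Report the group main effect with its 95% CI as overall compliance. State that the target is this average difference and not the group-by-time interaction tested for the neighbouring outcomes.

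State the assumption too: missingness depends only on observed data. If children who stop wearing the brace also stop replying, the mixed model can be biased as well, so the number of reports returned by arm and month should be shown beside the estimate.

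The cost is one or two sentences. The data and type of model are already in use for the OxAFQ-C and VAS, and sample size and the primary analysis are unaffected.
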